10.2.3.2. Causality

The Investigator will assess the causality/relationship between the study treatment and the AE.

The Investigator determines if there is a “reasonable possibility” that the study treatment caused the event (causality would be considered as related). Reasonable possibility is defined as evidence to suggest a causal relationship between the study treatment and AE. One of the following categories should be selected based on good medical and scientific judgment, considering the definitions in [Table 19](#) and all contributing factors.

Table 19: Causality Assessment Categories

For the purposes of regulatory reporting, if the Investigator chooses one of the following categories, the AE will be identified as “related by the Investigator.”	
Related	A clinical event, including laboratory test abnormality that occurs in a plausible time relationship to treatment administration, and which concurrent disease or other drugs or chemicals cannot explain. Biological plausibility or causality mechanism should be considered when assessing events as related. The response to withdrawal of the treatment (dechallenge ^a) should be clinically plausible. The event must be definitive pharmacologically or phenomenologically, using a satisfactory rechallenge ^b procedure if necessary.
Probably Related	A clinical event, including laboratory test abnormality, with a reasonable time sequence to administration of the treatment, unlikely to be attributed to concurrent disease or other drugs or chemicals, and which follows a clinically reasonable response on withdrawal (dechallenge). Rechallenge ^b information is not required to fulfill this definition.
Possibly Related	A clinical event, including laboratory test abnormality, with a reasonable time sequence to administration of the treatment, but which could also be explained by concurrent disease or other drugs or chemicals. Information on treatment withdrawal may be lacking or unclear.
If the Investigator chooses one of the following below, the AE will be identified as “not related by the Investigator.”	
Unlikely Related	A clinical event, including laboratory test abnormality, with a temporal relationship to treatment administration that makes a causal relationship improbable, and in which other drugs, chemicals, or underlying disease provide plausible explanations.
Not Related	A clinical event, including laboratory test abnormality, with little or no temporal relationship with treatment administration. May have negative dechallenge and rechallenge information. Typically explained by extraneous factors (eg, concomitant disease, environmental factors, or other drugs or chemicals).

^a Dechallenge is when a drug suspected of causing an AE is discontinued. If the symptoms of the AE disappear partially or completely, within a reasonable time from drug discontinuation, this is termed a positive dechallenge. If the symptoms continue despite withdrawal of the drug, this is termed a negative dechallenge. Note that there are exceptions when an AE does not disappear upon discontinuation of the drug, yet drug-relatedness clearly exists (for example, as in bone marrow suppression, fixed drug eruptions, or tardive dyskinesia).

^b Rechallenge is when a drug suspected of causing an AE in a specific subject in the past is readministered to that subject. If the AE recurs upon exposure, this is termed a positive rechallenge. If the AE does not recur, this is termed a negative rechallenge.

10.2.3.3. Action Taken

Action taken with the study drug will be defined as one of the following:

- Dose not changed
- Dose reduced
- Drug interrupted
- Drug withdrawn
- Not applicable

10.2.3.4. Outcome

Outcome will be defined as one of the following:

- Not recovered or not resolved
- Recovered or resolved
- Recovered or resolved with sequelae
- Recovering or resolving
- Fatal
- Unknown

10.3. Evaluation of Subjects Who Experience an Adverse Event during the Study

Subjects who experience an AE during the study will be evaluated to determine the outcome of the event. The clinical course of the event will be followed, according to the accepted standards of medical practice, until one of the following conditions is met:

1. Resolution
2. The event has stabilized
3. The subject withdrew consent or was lost to follow-up

For all AEs, the date and time of onset and resolution must be captured, if known. This is especially important for CRS, CRS-like events, neurotoxicity, or any infusion reactions. Onset and resolution times must be captured for these events. Failure to record these data will result in a deviation. All SAEs that are continuing at the completion of the study must be followed to determine outcome, as defined previously, to adequately evaluate the subject's safety.

In addition, any procedures performed and medications given to treat the AE(s) (details to include medication name, start date and time, stop date and time, dose, route, frequency, and reason for administration) should be recorded.

10.4. Pregnancy and Breastfeeding

10.4.1. Reporting of Pregnancy

The teratogenic potential of plamotamab is unknown. During the study, and for 6 months (male subjects) and 8 months (female subjects) after the last dose of plamotamab, lenalidomide, and/or tafasitamab, all women of childbearing potential or any partner of a male subject must be instructed to contact the Investigator immediately if pregnancy is suspected. Pregnancy in a subject or partner of a male subject who is receiving treatment should be reported following procedures for an SAE

(although it will not be labeled as an SAE). The pregnancy event will be recorded on the pregnancy report form. Elective abortions without complications should not be reported as AEs.

If pregnancy is suspected in a subject prior to study treatment administration, the study treatment must be withheld until the β -hCG test result is available. If pregnancy is confirmed, the subject must not receive study treatment and must be withdrawn from the study. If pregnancy is suspected while the subject is receiving study treatment, the study treatment must be immediately withheld until the result of a β -hCG test result is available. If pregnancy is confirmed, the subject will be permanently discontinued from the study in an appropriate manner.

The Investigator must immediately notify the Sponsor of any pregnancy that occurs in subjects during study treatment exposure and for at least 8 months after drug administration for female subjects and 6 months for sexual partners of male subjects. Protocol-required procedures for study discontinuation must be performed unless contraindicated by pregnancy (eg, X-ray studies). Other appropriate follow-up procedures should be considered, if indicated. The outcome of all pregnancies (spontaneous miscarriage, elective termination, normal birth, or congenital abnormality) must be followed up and documented to the Sponsor even if the subject was discontinued from the study. The follow-up period will be deemed to have ended when the health status of the child has been determined on its birth.

All outcomes of pregnancy must be reported by the Investigator to the Sponsor and ICON PLC on the pregnancy outcome report form within 30 days after he/she has gained knowledge of the normal delivery or elective abortion and approximately 30 calendar days postpartum.

Any SAE that occurs during pregnancy must be recorded on the SAE report form (eg, maternal serious complications, therapeutic abortion, ectopic pregnancy, stillbirth, neonatal death, congenital anomaly, birth defect) and reported within 24 hours of awareness in accordance with the procedure for reporting SAEs. All reports of congenital abnormalities/birth defects are SAEs. Spontaneous miscarriages should also be reported and handled as SAEs. Infants should be monitored for a minimum of 8 weeks after birth.

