6.3. Subject Withdrawal Criteria

6.3.1. Criteria for Removal from Study Treatment

A subject may withdraw from the study treatment at any time at his/her own request, or may be withdrawn at any time at the discretion of the Investigator for any of the following reasons:

- Disease progression
- Occurrence of an unacceptable AE
- Investigator decision
- Subject non-compliance with study drug
- Death

- Administrative reasons
- Other

Subjects must be withdrawn from treatment if the beta human chorionic gonadotropin (β -HCG) pregnancy test is consistent with pregnancy. Before permanent study treatment discontinuation, the treatment may be interrupted to confirm the positive pregnancy test. Pregnancy should be reported as described in [Section 10.4](#). Subjects with a confirmed positive pregnancy test will continue in the follow-up phase of the study.

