6.3.2. Criteria for Removal from Study

The subject is considered to be off study for any of the following reasons:

- Screen failure
- Completed study follow-up period of 5 years
- Subject requests to be withdrawn from study and any follow-up
- Death

Whenever possible, the Sponsor must be notified within 24 hours if a subject is withdrawn from treatment and/or study. The reason(s) for a subject's discontinuation from the treatment and study are to be reported to the Sponsor and recorded in the source documents and the subject's eCRF. For subjects who withdraw their consent from the study, this must be clearly documented in their subject source documents with confirmation that no further follow-up and data may be collected.

The EOT and end-of-study (EOS) termination pages in the eCRF must be completed for all subjects who discontinue permanently.

For subjects who discontinue study treatment, all assessments described for the EOT visit should be performed at the scheduled visit dates (if at all possible). Subjects who complete a tumor assessment within 14 days of EOT do not have to repeat the EOT tumor assessment. Complete the EOS eCRF and any follow-up forms at the time of screen failure, death, or withdrawal of consent.

If it is possible, perform all assessments as close to the scheduled dates as is practicable. Post-treatment evaluations should attempt to be completed no later than approximately 4 weeks after the final dose administration and prior to initiation of a new treatment for the malignancy.

Subjects who are withdrawn for any reason may not re-enter this study. The Study Sponsor, Xencor, reserves the right to terminate this clinical study at any time and for any reason.

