7.6. Treatment Evaluations

7.6.1. Treatment Cycles

The schedule of required procedures and clinical site study days for each cycle is detailed in [Table 9](#), [Table 10](#), and [Table 11](#). The day prior to C1D1 is Day -1. Subjects in Part 1 and subjects randomized into Arm A of Part 2 will be admitted to an inpatient facility and monitored for a minimum of 72 hours following dosing for the first dose of plamotamab and for 24 hours following any subsequent dose escalation.

After discontinuation of treatment, subjects will be followed for PFS and OS every 2 months by telephone, email, or mail contact by the site up to 5 years or until death.

Study days for required procedures are specified in the Schedule of Assessments (Table 9). The procedures include the following:

Clinical Assessments: Clinical assessments include the following:

- Abbreviated (study-related) medical history
- PE, including weight and tumor assessment (examination of skin, head, eyes, ears, neck, and throat [HEENT], bidimensional measurement of cervical, supraclavicular, axillary, and inguinal lymph nodes, spleen size [below costal margin], heart, chest, lungs, abdomen, extremities, neurologic, and back).
- Neurologic examination will be assessed using the ASTCT ICANS Consensus Grading for Adults (see Section 4.6.1.7)
- Vital signs (supine or sitting position, including blood pressure, heart rate, respirations, temperature, and blood oxygen saturation by continuous pulse oximetry)
 - For tafasitamab infusion, vital signs and clinical assessment for AEs are monitored during and after the end of the infusion. Timepoints include the following: predose and 30 (\pm 5) minutes after end of infusion (EOI).

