7.6.4. Long-Term Follow-Up Period

All subjects will be followed for progression and OS approximately every 2 months (\pm 2 weeks) after the 90-day follow-up visit (see [Section 7.6.3](#)) visit. This includes subjects who discontinue treatment due to progression or toxicity, as well as those who discontinue before progression to pursue a new anti-lymphoma/salvage therapy (chemotherapy, SCT, radiotherapy, etc.). Subjects who discontinue due to toxicity and without progression will continue to have efficacy assessments performed until progression or the initiation of new therapy. Subjects will be contacted by telephone, email, or mail contact by the site until death or 5 years from randomization. The following data will be collected at each follow-up contact:

- Survival status date and cause of death (if applicable)
- Transplantation date and other transplant related outcomes (if applicable)
- Date of progression
- subsequent treatments and efficacy outcomes of those treatments
- date of last confirmation of survival (last know date alive)

It is anticipated that the information will be available from the treating Investigator, oncologist, primary care physician, local medical records, or the subject. The Investigator may search public sources for status information. Completion of the long-term follow-up period is required for any randomized subject, even if the subject did not receive the intervention. The duration of follow-up on this trial may be modified based on observed subject outcomes, ie, lengthened if significant numbers of durable responses are seen or shortened if few subjects require long follow-up.

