Nonmeasured lesions: Any disease not selected as measured, dominant disease and truly assessable disease should be considered not measured. These sites include any nodes, nodal masses, and extranodal sites not selected as dominant or measurable or that do not meet the requirements for measurability but are still considered abnormal, as well as truly assessable disease, which is any site of suspected disease that would be difficult to follow quantitatively with measurement, including pleural effusions, ascites, bone lesions, leptomeningeal disease, abdominal masses, and other lesions that cannot be confirmed and followed by imaging.

- ^a In Waldeyer’s ring or in extranodal sites (eg, GI tract, liver, bone marrow), FDG uptake may be greater than in the mediastinum with complete metabolic response but should be no higher than surrounding normal physiologic uptake (eg, with marrow activation as a result of chemotherapy or myeloid growth factors).
- ^b PET 5PS: 1, no uptake above background; 2, uptake ≤ mediastinum; 3, uptake > mediastinum but ≤ liver; 4, uptake moderately > liver; 5, uptake markedly higher than liver and/or new lesions; X, new areas of uptake unlikely to be related to lymphoma.

The Investigator and the BIRC will assess response to study drug at each efficacy timepoint. The following endpoints will be reported:

Progression-free Survival: defined as the time from randomization to the first documentation of progressive disease or death, whichever comes first. The Investigator and the BIRC will determine the progressive disease event in all randomized subjects.

Duration of Response: defined as the time from the first response (CR or PR) to progression or death due to any cause among subjects achieving a CR or PR and among CR subjects. DOR will be derived using disease progression as determined by the BIRC in subjects who have a response (CR or PR).

Overall Survival: defined as the time from randomization to death from any cause. All randomized subjects will be followed for up to 5 years for survival.

Time to Treatment Failure: defined as the time from randomization to discontinuation of all study treatment for any reason, including disease progression, treatment toxicity, and death. The time to treatment failure will be using disease progression as determined by the Investigator and by the BIRC.

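### Protocol Section 10.4.1 takes a subject with confirmed pregnancy off the study, while Section 6.3.1 keeps her in follow-up; minor, and wrong as written

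*Protocol*

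**What the plan says.** Section 10.4.1 (Reporting of Pregnancy) has two rules.

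- **Pregnancy confirmed before study treatment:** "If pregnancy is confirmed, the subject must not receive study treatment and must be withdrawn from the study".
- **Pregnancy confirmed on study treatment:** "If pregnancy is confirmed, the subject will be permanently discontinued from the study in an appropriate manner".

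The next paragraph of 10.4.1 adds that pregnancy outcomes "must be followed up and documented to the Sponsor even if the subject was discontinued from the study".

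Other sections of the Protocol read differently.

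- **6.3.1:** a positive test means withdrawal from treatment, and then "Subjects with a confirmed positive pregnancy test will continue in the follow-up phase of the study".
- **6.3.2:** a list introduced by "The subject is considered to be off study for any of the following reasons" has four entries: screen failure, completion of the 5-year follow-up, the subject's own request, and death. Pregnancy is not among them.
- **7.6.1:** "After discontinuation of treatment, subjects will be followed for PFS and OS every 2 months".
- **7.6.4:** "Completion of the long-term follow-up period is required for any randomized subject, even if the subject did not receive the intervention".
- **9.1:** "All randomized subjects will be followed for up to 5 years for survival".

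**The concern.** Two sections give incompatible instructions for one event. Neither says which prevails, and 10.4.1 does not refer back to 6.3.1.

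The statistical interest lies in Part 2. The primary estimand (Section 11.2, Table 20) covers all randomized Part 2 subjects, lists discontinuation of treatment as an intercurrent event, and handles it by treatment policy. That strategy needs follow-up to continue after treatment stops. A site that opened 10.4.1 on a positive test and followed it to the letter could stop collecting progression and survival data on a randomized subject. She would then be censored for a reason that the rest of the protocol does not recognize.

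**Working it through.** The main check is a comparison of texts; a short calculation then puts the size in context.

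**1. Same event, opposite study status.** Both 10.4.1 and 6.3.1 address a confirmed pregnancy in a subject on treatment. Both stop the drug. On study status, 10.4.1 removes her and 6.3.1 keeps her in follow-up. This is the one express contradiction.

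**2. Which way the rest of the protocol points.** Section 6.3.2 supports 6.3.1 by omission. Sections 7.6.1, 7.6.4 and 9.1 support it as general follow-up rules with no exception for pregnancy.

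**3. Could the study be shorthand for study treatment in 10.4.1?** This reading is hard to sustain.
- The same paragraph says study treatment when it means the drug, in the instruction to withhold it pending the test result.
- The next paragraph speaks of the procedures required at study discontinuation.
- It then preserves pregnancy-outcome follow-up "must be followed up and documented to the Sponsor even if the subject was discontinued from the study", a clause needed only if the subject really is off study.
- The remaining sentence on other follow-up is discretionary and does not restore progression or survival follow-up.

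**4. The pre-treatment rule.** Withdrawal from the study is right for a subject who fails screening, and 6.3.2 agrees. It is wrong for a subject already randomized, and the Part 2 schedule makes that case foreseeable:

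| Step | Timing | Source |
|---|---|---|
| Randomization | Day -10/-9 | Section 7.5.1 |
| Pregnancy test | Day -8, before the first dose | Sections 6.4 and 7.5.1; Table 9 |
| Intent-to-treat set | Everyone randomized into Part 2 | Section 11.5 |

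A woman who tests positive on Day -8 is therefore in the intent-to-treat set and untreated. That is the kind of subject whom 7.6.4 requires to be followed.

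**5. Size.** The documents give no pregnancy rate, so the effect of this wording cannot be calculated. The losses that the design already allows for can be.

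Inputs from Sections 11.3.1 and 11.3.2:
- 200 subjects, 100 per arm, accrued over A = 27 months;
- PFS medians of 12 and 23.5 months, loss of 1.5% per month, analysis at T = 33 months;
- OS median of 34 months in Arm B and HR 0.60 (so 34/0.60 = 56.7 months in Arm A), loss of about 1% per month, analysis at T = 51 months.

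Exponential times and uniform accrual are assumed. With h = ln 2/median, d = -ln(1 - monthly loss) and s = h + d:

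- share with an event or lost by T: q = 1 - [exp(-s(T - A)) - exp(-sT)]/(sA)
- P(event) = (h/s)q and P(lost) = (d/s)q

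| Analysis | Planned events | Events, this model | Losses, this model |
|---|---|---|---|
| PFS, month 33 | 93 | 93.6 | 33.7 |
| OS, month 51 | 76 | 75.7 | 47.4 |

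The model reproduces the planned event counts. The design thus already tolerates about 34 losses for PFS and 47 for OS. Both analyses are triggered by events, so an isolated extra loss would at most delay them slightly.

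**The case against.** The strongest reply has four parts.

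- **Only 6.3.1 names pregnancy.** The other sections are general rules, to which a specific pregnancy rule could be an exception, and the 6.3.2 list is not stated to be exhaustive. This is fair as to weight, but the direct conflict with 6.3.1 remains.
- **The layout suggests that 6.3.1 governs.** It sits under the withdrawal criteria and sends the reader to 10.4 only for reporting. This makes the error less likely in practice. It does not correct an instruction that says the opposite.
- **The link to the primary endpoint is limited.** Progression by the blinded review committee needs scans. Section 10.4.1 excuses discontinuation procedures contraindicated in pregnancy, with X-ray studies as its example. Section 7.6.4 expressly continues efficacy assessments only for subjects who stop for toxicity without progression. Centrally read progression could therefore go unobserved under either wording. This stands. What the correct rule secures is the two-monthly contact by telephone, email or mail, which captures deaths (events for both PFS and OS) and reported progression dates. Pregnancy is no reason to stop that contact.
- **The harm is hypothetical.** Part 2 could start only after at least 40 Part 1 subjects had been evaluated, and the SAP (Section 1) reports 3 enrolled, with listings only. This is correct, and it limits the point to reuse of the text.

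**Conclusion.** The concern holds: this is an internal inconsistency, wrong as written and minor. Section 10.4.1 orders removal from the study where 6.3.1 orders continued follow-up, and the rest of the protocol supports 6.3.1. The pre-treatment sentence is wrong only for a Part 2 subject who has already been randomized.

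The effect is negligible. No loss of power, of safety data or of pregnancy-outcome follow-up is claimed, and no gap in scans is attributed to this wording. The conclusion on the text needs no numerical assumption. The judgement on size rests on pregnancies being very rare under the contraception and testing rules, on the model assumptions stated in the working, and on the study having ended without any efficacy analysis.

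**What to change.** Change two sentences in Section 10.4.1.

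1. **On treatment:** state that the subject permanently stops study treatment, and that progression, survival and pregnancy-outcome follow-up continue under Sections 6.3.1 and 7.6.4 unless she withdraws consent.
2. **Before treatment:** keep withdrawal from the study for subjects not yet enrolled (Part 1) or not yet randomized (Part 2). Add that a Part 2 subject already randomized, such as one with a positive Day -8 test, receives no study treatment and stays in follow-up under Section 7.6.4.

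Sections 6.3.2 and 7.6.4 need no change. The cost is close to nil: the protocol was due for revision before Part 2 (Section 4.1.2) to set the dosing regimen, and that revision could have carried the edit. With the study terminated, the change is worth making only if this text is used again.
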